10.0 Quality Control and Quality Assurance

- The study is low risk; therefore, we do not anticipate any serious adverse events from the acupuncture intervention. The PI will provide oversight for the de-identification of the data. The PI will review all data collection forms on an ongoing basis for: data completeness, data accuracy and protocol compliance.

11.0 Data and Safety Monitoring

- The study is low risk. However, the research team will monitor the safety of subjects during study procedures. In the event of injury related to this research, treatment will be available through the UIC Medical Center. However, the patient or third party payer, if any, will be responsible for payment of this treatment. Patient subjects will remain under the care of their usual provider, who will be available to give them usual care if needed. Any unanticipated problems related to the study procedure will be immediately reported to the IRB.
- Data Security: Each participant will be assigned a code number and their data will be identified only with that code number. Only the PI will have access to the code/master key. All questionnaires will be collected on paper and stored in a locked cabinet in the locked PI's office.

12.0 Statistical Considerations

- This is a feasibility study and has not been powered. The data will be descriptive in nature.

13.0 Regulatory Requirements

13.1 Informed Consent

- Informed consent will be obtained either by the PI or other key research personnel who have obtained IRB and HIPAA certifications. The RA will have been trained by the PI on the informed consent procedures. It will be obtained on paper.
- The consent process will be completed in person and in a private area at either the UIH SCD Clinic or the acupuncture exam rooms on the 2nd floor CON.

- Subjects will be informed that they will receive 2 acupuncture treatments for 30 minutes each week for 5 weeks, for a total of 10 treatments.
- Informed consent documents will be stored in a locked file cabinet in the locked PI's office. The study team will have access to the informed consent documents.

13.2 Subject Confidentiality

- All measures will be completed in a private exam room with soundproof walls on the 2nd floor of the UIC CON.
- The link between the research data and code number will be destroyed after all manuscripts are published.

13.3 Unanticipated Problems

- Any unanticipated problems related to the study procedure will be immediately reported to the IRB.

APPENDIX A:

Acupuncture for Adults with Sickle Cell Disease (SCD): A Feasibility Study Eligibility Checklist

Yes No

Inclusion criteria:

- ≥18 years-old with a diagnosis of SCD
- Had a moderate to severe level of pain (≥ 3 on 0-10 scale) related to SCD within the last 3 months
- Speaks/reads English
- Receiving care at the UI Health SCD clinic

Exclusion criteria:

- Pregnant
- Physically or cognitively unable to complete the study procedures

APPENDIX B, MEASURES:

Demographic Measures

Sickle Cell Disease Participant Characteristics

Variable	Category
How old are you	
What is your marital status	Single
	Married/Partnered
	White
What is your race	Black/African-American
	Native American/Alaska Native
	Hispanic
What is your income	<40k
	40-50k
	50k+
How much education have you had?	< HS, HS, Vocational School
	Some college or Associates degree
	Bachelor's degree or higher

Pain Intensity – Scale

Please respond to each item by marking one box per row.

In the past 7 days...		Had no pain	Mild	Moderate	Severe	Very severe
PAINQ16	How intense was your pain at its worst?....	 1	 2	 3	 4	 5
PAINQ19	How intense was your average pain?.....	 1	 2	 3	 4	 5
		No pain	Mild	Moderate	Severe	Very severe
PAINQ21	What is your level of pain right now?.....	 1	 2	 3	 4	 5

Global Health**Please respond to each question or statement by marking one box per row.**

		Excellent	Very good	Good	Fair	Poor
Global01	In general, would you say your health is:	 5	 4	 3	 2	 1
Global02	In general, would you say your quality of life is:.....	 5	 4	 3	 2	 1
Global03	In general, how would you rate your physical health?	 5	 4	 3	 2	 1
Global04	In general, how would you rate your mental health, including your mood and your ability to think?	 5	 4	 3	 2	 1
Global05	In general, how would you rate your satisfaction with your social activities and relationships?	 5	 4	 3	 2	 1
Global09r	In general, please rate how well you carry out your usual social activities and roles. (This includes activities at home, at work and in your community, and responsibilities as a parent, child, spouse, employee, friend, etc.).....	 5	 4	 3	 2	 1
Global06	To what extent are you able to carry out your everyday physical activities such as walking, climbing stairs, carrying groceries, or moving a chair?	 5	 4	 3	 2	 1
		Completely	Mostly	Moderately	A little	Not at all

In the past 7 days...		Never	Rarely	Sometimes	Often	Always						
Global01r	How often have you been bothered by emotional problems such as feeling anxious, depressed or irritable?	 5	 4	 3	 2	 1						
Global02r	How would you rate your fatigue on average?	 5	 4	 3	 2	 1						
Global07r	How would you rate your pain on average?	 0 No pain	 1	 2	 3	 4	 5	 6	 7	 8	 9	 10 Worst pain imaginable

Pain Interference

Please respond to each item by marking one box per row.

In the past 7 days...

		Not at all	A little bit	Somewhat	Quite a bit	Very much
PAIN11	How difficult was it for you to take in new information because of pain?	 1	 2	 3	 4	 5
PAIN12	How much did pain interfere with your enjoyment of life?	 1	 2	 3	 4	 5
PAIN13	How much did pain interfere with your ability to participate in leisure activities?	 1	 2	 3	 4	 5
PAIN14	How much did pain interfere with your close personal relationships?	 1	 2	 3	 4	 5
PAIN15	How much did pain interfere with your ability to concentrate?	 1	 2	 3	 4	 5
PAIN16	How much did pain interfere with your day to day activities?	 1	 2	 3	 4	 5
PAIN17	How much did pain interfere with your enjoyment of recreational activities?	 1	 2	 3	 4	 5

In the past 7 days...

		Not at all	A little bit	Somewhat	Quite a bit	Very much
PAININ11	How often did you feel emotionally tense because of your pain?.....	 1	 2	 3	 4	 5
PAININ12	How much did pain interfere with the things you usually do for fun?	 1	 2	 3	 4	 5
PAININ13	How much did pain interfere with your family life?.....	 1	 2	 3	 4	 5
PAININ17	How much did pain interfere with your relationships with other people?	 1	 2	 3	 4	 5
PAININ18	How much did pain interfere with your ability to work (include work at home)?	 1	 2	 3	 4	 5
PAININ19	How much did pain make it difficult to fall asleep?.....	 1	 2	 3	 4	 5
PAININ20	How much did pain feel like a burden to you?.....	 1	 2	 3	 4	 5
PAININ22	How much did pain interfere with work around the home?.....	 1	 2	 3	 4	 5

In the past 7 days...

		Not at all	A little bit	Somewhat	Quite a bit	Very much
PAININ31	How much did pain interfere with your ability to participate in social activities?	 1	 2	 3	 4	 5
PAININ34	How much did pain interfere with your household chores?.....	 1	 2	 3	 4	 5
PAININ35	How much did pain interfere with your ability to make trips from home that kept you gone for more than 2 hours?.....	 1	 2	 3	 4	 5
PAININ36	How much did pain interfere with your enjoyment of social activities?.....	 1	 2	 3	 4	 5
PAININ48	How much did pain interfere with your ability to do household chores?.....	 1	 2	 3	 4	 5
PAININ49	How much did pain interfere with your ability to remember things?.....	 1	 2	 3	 4	 5
PAININ56	How irritable did you feel because of pain?.....	 1	 2	 3	 4	 5
PAININ14	How much did pain interfere with doing your tasks away from home (e.g., getting groceries, running errands)?.....	 1	 2	 3	 4	 5

In the past 7 days...

		Never	Rarely	Sometimes	Often	Always
PAININ16	How often did pain make you feel depressed?.....	 1	 2	 3	 4	 5
PAININ24	How often was pain distressing to you?	 1	 2	 3	 4	 5
PAININ26	How often did pain keep you from socializing with others?.....	 1	 2	 3	 4	 5
PAININ29	How often was your pain so severe you could think of nothing else?.....	 1	 2	 3	 4	 5
PAININ32	How often did pain make you feel discouraged?	 1	 2	 3	 4	 5
PAININ37	How often did pain make you feel anxious?	 1	 2	 3	 4	 5
PAININ38	How often did you avoid social activities because it might make you hurt more?	 1	 2	 3	 4	 5
PAININ40	How often did pain prevent you from walking more than 1 mile?.....	 1	 2	 3	 4	 5
PAININ42	How often did pain prevent you from standing for more than one hour?	 1	 2	 3	 4	 5

In the past 7 days...					
		Never	Rarely	Sometimes	Often
		1	2	3	4
		5			
PAININ46	How often did pain make it difficult for you to plan social activities?				
PAININ47	How often did pain prevent you from standing for more than 30 minutes?				
PAININ60	How often did pain prevent you from sitting for more than 30 minutes?				
PAININ61	How often did pain prevent you from sitting for more than 10 minutes?				
PAININ52	How often was it hard to plan social activities because you didn't know if you would be in pain?				
PAININ53	How often did pain restrict your social life to your home?				
PAININ55	How often did pain prevent you from sitting for more than one hour?				
In the past 7 days...					
		Never	Once a week or less	Once every few days	Once a day
		1	2	3	4
		5			
PAININ54	How often did pain keep you from getting into a standing position?				

LEVEL 2—Depression—Adult*
 *PROMIS Emotional Distress—Depression—Short Form

Name: _____ Age: _____ Sex: Male Female Date: _____

If the measure is being completed by an informant, what is your relationship with the individual receiving care? _____

In a typical week, approximately how much time do you spend with the individual receiving care? _____ hours/week

Instructions: On the DSM-5 Level 1 cross-cutting questionnaire that you just completed, you indicated that *during the past 2 weeks* you (the individual receiving care) have been bothered by “no interest or pleasure in doing things” and/or “feeling down, depressed, or hopeless” at a mild or greater level of severity. The questions below ask about these feelings in more detail and especially how often you (the individual receiving care) have been bothered by a list of symptoms during the past 7 days. Please respond to each item by marking (✓ or x) one box per row.

						Clinician Use
						Item Score
In the past SEVEN (7) DAYS....						
	Never	Rarely	Sometimes	Often	Always	
1. I felt worthless.	 1	 2	 3	 4	 5	
2. I felt that I had nothing to look forward to.	 1	 2	 3	 4	 5	
3. I felt helpless.	 1	 2	 3	 4	 5	
4. I felt sad.	 1	 2	 3	 4	 5	
5. I felt like a failure.	 1	 2	 3	 4	 5	
6. I felt depressed.	 1	 2	 3	 4	 5	
7. I felt unhappy.	 1	 2	 3	 4	 5	
8. I felt hopeless.	 1	 2	 3	 4	 5	
Total/Partial Raw Score:						
Prorated Total Raw Score:						
T-Score:						

©2008-2012 PROMIS Health Organization (PHO) and PROMIS Cooperative Group.
 This material can be reproduced without permission by clinicians for use with their patients.
 Any other use, including electronic use, requires written permission of the PHO.

Emotional Distress - Anxiety – Calibrated Items**Please respond to each item by marking one box per row.****In the past 7 days...**

		Never	Rarely	Sometimes	Often	Always
EDANX01	I felt fearful.....	 1	 2	 3	 4	 5
EDANX02	I felt frightened.....	 1	 2	 3	 4	 5
EDANX03	It scared me when I felt nervous	 1	 2	 3	 4	 5
EDANX05	I felt anxious.....	 1	 2	 3	 4	 5
EDANX07	I felt like I needed help for my anxiety	 1	 2	 3	 4	 5
EDANX08	I was concerned about my mental health ...	 1	 2	 3	 4	 5
EDANX12	I felt upset.....	 1	 2	 3	 4	 5
EDANX13	I had a racing or pounding heart.....	 1	 2	 3	 4	 5
EDANX16	I was anxious if my normal routine was disturbed.....	 1	 2	 3	 4	 5

In the past 7 days...

		Never	Rarely	Sometimes	Often	Always
		1	2	3	4	5
EDANX10	I had sudden feelings of panic.....					
EDANX20	I was easily startled					
EDANX21	I had trouble paying attention.....					
EDANX24	I avoided public places or activities					
EDANX26	I felt fidgety.....					
EDANX27	I felt something awful would happen.....					
EDANX30	I felt worried.....					
EDANX33	I felt terrified					
EDANX37	I worried about other people's reactions to me					
EDANX40	I found it hard to focus on anything other than my anxiety					

27 April 2016

© 2008-2016 PROMIS Health Organization and PROMIS Cooperative Group

Page 2 of 3

In the past 7 days...		Never	Rarely	Sometimes	Often	Always
EDANX41	My worries overwhelmed me	 1	 2	 3	 4	 5
EDANX44	I had twitching or trembling muscles	 1	 2	 3	 4	 5
EDANX46	I felt nervous	 1	 2	 3	 4	 5
EDANX47	I felt indecisive.....	 1	 2	 3	 4	 5
EDANX48	Many situations made me worry.....	 1	 2	 3	 4	 5
EDANX49	I had difficulty sleeping	 1	 2	 3	 4	 5
EDANX51	I had trouble relaxing.....	 1	 2	 3	 4	 5
EDANX53	I felt uneasy.....	 1	 2	 3	 4	 5
EDANX54	I felt tense.....	 1	 2	 3	 4	 5
EDANX55	I had difficulty calming down.....	 1	 2	 3	 4	 5

Emotional Distress - Anger – Short Form 5a

Please respond to each item by marking one box per row.

In the past 7 days...

		Never 1	Rarely 2	Sometimes 3	Often 4	Always 5
EDANG03	I was irritated more than people knew ...					
EDANG09	I felt angry					
EDANG15	I felt like I was ready to explode					
EDANG30	I was grouchy					
EDANG35	I felt annoyed.....					

Sleep Disturbance – Calibrated Items**Please respond to each item by marking one box per row.****In the past 7 days...**

		Not at all	A little bit	Somewhat	Quite a bit	Very much
Sleep105	My sleep was restful.....	 5	 4	 3	 2	 1
Sleep106	My sleep was light.....	 1	 2	 3	 4	 5
Sleep107	My sleep was deep.	 5	 4	 3	 2	 1
Sleep108	My sleep was restless.....	 1	 2	 3	 4	 5
Sleep115	I was satisfied with my sleep.....	 5	 4	 3	 2	 1
Sleep116	My sleep was refreshing.....	 5	 4	 3	 2	 1
Sleep125	I felt lousy when I woke up.....	 1	 2	 3	 4	 5
Sleep20	I had a problem with my sleep.	 1	 2	 3	 4	 5
Sleep44	I had difficulty falling asleep.....	 1	 2	 3	 4	 5
Sleep65	I felt physically tense at bedtime.....	 1	 2	 3	 4	 5

28 April 2016

© 2008-2015 PROMIS Health Organization and PROMIS Cooperative Group

Page 1 of 3

In the past 7 days...

		Not at all	A little bit	Somewhat	Quite a bit	Very much
Sleep67	I worried about not being able to fall asleep.....	 1	 2	 3	 4	 5
Sleep68	I felt worried at bedtime.....	 1	 2	 3	 4	 5
Sleep69	I had trouble stopping my thoughts at bedtime.....	 1	 2	 3	 4	 5
Sleep70	I felt sad at bedtime.....	 1	 2	 3	 4	 5
Sleep71	I had trouble getting into a comfortable position to sleep.....	 1	 2	 3	 4	 5
Sleep72	I tried hard to get to sleep.....	 1	 2	 3	 4	 5
Sleep78	Stress disturbed my sleep.....	 1	 2	 3	 4	 5
Sleep86	I tossed and turned at night.....	 1	 2	 3	 4	 5
Sleep93	I was afraid I would not get back to sleep after waking up.....	 1	 2	 3	 4	 5

In the past 7 days...

		Never	Rarely	Sometimes	Often	Always
Sleep110	I got enough sleep.....	 5	 4	 3	 2	 1
Sleep42	It was easy for me to fall asleep.....	 5	 4	 3	 2	 1
Sleep45	I laid in bed for hours waiting to fall asleep.....	 1	 2	 3	 4	 5
Sleep50	I woke up too early and could not fall back asleep.	 1	 2	 3	 4	 5
Sleep07	I had trouble staying asleep.....	 1	 2	 3	 4	 5
Sleep00	I had trouble sleeping.....	 1	 2	 3	 4	 5
Sleep92	I woke up and had trouble falling back to sleep.	 1	 2	 3	 4	 5
In the past 7 days...						
		Very poor	Poor	Fair	Good	Very good
Sleep109	My sleep quality was...	 5	 4	 3	 2	 1

Fatigue – Short Form 6a**Please respond to each question or statement by marking one box per row.****During the past 7 days...**

		Not at all	A little bit	Somewhat	Quite a bit	Very much
1	I feel fatigued					
2	I have trouble starting things because I am tired.....					
	In the past 7 days...					
3	How run-down did you feel on average? ...					
4	How fatigued were you on average?					
5	How much were you bothered by your fatigue on average?.....					
6	To what degree did your fatigue interfere with your physical functioning?.....					

General Self-Efficacy – Short Form 4a**Please respond to each item by marking one box per row.**

For the next set of questions, please read each sentence and rate your level of confidence in managing various situations, problems, and events.

Rate your level of confidence.		I am not at all confident	I am a little confident	I am somewhat confident	I am quite confident	I am very confident
1	GSE11_0 I can manage to solve difficult problems if I try hard enough.	 1	 2	 3	 4	 5
2	GSE14_0 I am confident that I could deal efficiently with unexpected events.	 1	 2	 3	 4	 5
3	GSE19_0 If I am in trouble, I can think of a solution.	 1	 2	 3	 4	 5
4	GSE20_0 I can handle whatever comes my way.....	 1	 2	 3	 4	 5

Ψ Injustice Experience Questionnaire

Copyright © 2002
Michael JL Sullivan

IEQ

Name: _____ Age: _____ Gender: _____ Date: _____

When injuries happen, they can have profound effects on our lives. This scale was designed to assess how your injury has affected your life.

Listed below are twelve statements describing different thoughts and feelings that you may experience when you think about your injury. Using the following scale, please indicate how frequently you experience these thoughts and feelings when you think about your injury.

0 – never 1 – rarely 2 – sometimes 3 – often 4 – all the time

- 1 Most people don't understand how severe my condition is.
- 2 My life will never be the same.
- 3 I am suffering because of someone else's negligence.
- 4 No one should have to live this way.
- 5 I just want to have my life back.
- 6 I feel that this has affected me in a permanent way.
- 7 It all seems so unfair.
- 8 I worry that my condition is not being taken seriously.
- 9 Nothing will ever make up for all that I have gone through.
- 10 I feel as if I have been robbed of something very precious.
- 11 I am troubled by fears that I may never achieve my dreams.
- 12 I can't believe this has happened to me.

...Total

Credibility/Expectancy QuestionnaireGroup Number _____
Study Identification Number _____
Number _____

Please answer each item by indicating the number that best describes your response.

1. At this point, how logical does the acupuncture seem to you?

1	2	3	4	5	6	7	8	9	10
not at all logical				somewhat logical					very logical

2. At this point, how useful do you think the acupuncture will be in reducing your pain?

1	2	3	4	5	6	7	8	9	10
not at all useful				somewhat useful					very useful

3. How confident would you be in recommending the acupuncture to a friend who experiences similar problems?

1	2	3	4	5	6	7	8	9	10
not at all confident				somewhat confident					very confident

4. By the end of the study period, how much improvement in your pain symptoms do you think will occur?

0% 10% 20% 30% 40% 50% 60% 70% 80% 90% 100%

For the last two questions, close your eyes for a few moments, and try to identify what you really feel about the acupuncture and its likely success. Then answer the following questions:

5. At this point, how much do you really *feel* that the acupuncture will help you to reduce your pain symptoms?

1	2	3	4	5	6	7	8	9	10
not at all				somewhat					very much

6. By the end of the study period, how much improvement in your pain symptoms do you really *feel* will occur?

0% 10% 20% 30% 40% 50% 60% 70% 80% 90% 100%

Ψ Pain Catastrophization Questionnaire

Copyright © 1995
Michael JL Sullivan

PCS-EN

Client No.: _____ Age: _____ Sex: M(____) F(____) Date: _____

Everyone experiences painful situations at some point in their lives. Such experiences may include headaches, tooth pain, joint or muscle pain. People are often exposed to situations that may cause pain such as illness, injury, dental procedures or surgery.

We are interested in the types of thoughts and feelings that you have when you are in pain. Listed below are thirteen statements describing different thoughts and feelings that may be associated with pain. Using the following scale, please indicate the degree to which you have these thoughts and feelings when you are experiencing pain.

0 – not at all 1 – to a slight degree 2 – to a moderate degree 3 – to a great degree 4 – all the time

When I'm in pain ...

- ₁ I worry all the time about whether the pain will end.
- ₂ I feel I can't go on.
- ₃ It's terrible and I think it's never going to get any better.
- ₄ It's awful and I feel that it overwhelms me.
- ₅ I feel I can't stand it anymore.
- ₆ I become afraid that the pain will get worse.
- ₇ I keep thinking of other painful events.
- ₈ I anxiously want the pain to go away.
- ₉ I can't seem to keep it out of my mind.
- ₁₀ I keep thinking about how much it hurts.
- ₁₁ I keep thinking about how badly I want the pain to stop.
- ₁₂ There's nothing I can do to reduce the intensity of the pain.
- ₁₃ I wonder whether something serious may happen.

... Total

Updated 11/11

Part 2: What Does Your Pain Feel Like?

Some of the words below describe your present pain. Circle ONLY those words that describe it. Leave out any category that is not suitable. Use only a single word on each appropriate category - the one that applies best.

1

Flickering
Quivering
Pulsing
Throbbing
Beating
Pounding

2

Jumping
Flashing
Shooting

3

Pricking
Boring
Drilling
Stabbing
Lancinating

4

Sharp
Cutting
Lacerating

5

Pinching
Pressing
Gnawing
Cramping
Crushing

6

Tugging
Pulling
Wrenching

7

Hot
Burning
Scalding
Searing

8

Tingling
Itchy
Smarting
Stinging

9

Dull
Sore
Hurting
Aching
Heavy

10

Tender
Taut
Rasping
Splitting

11

Tiring
Exhausting

12

Sickening
Suffocating

13

Fearful
Frightening
Terrifying

14

Punishing
Grueling
Cruel
Vicious
Killing

15

Wretched
Blinding
Intense

16

Annoying
Troublesome
Miserable
Unbearable

17

Spreading
Radiating
Penetrating
Piercing

18

Tight
Numb
Drawing
Squeezing
Tearing

19

Cool
Cold
Freezing

20

Nagging
Nauseating
Agonizing
Dreadful
Torturing

Part 3: How Does Your Pain Change with Time?

1. Which word or words would you use to describe the pattern of your pain?

1	2	3
Continuous	Rhythmic	Brief
Steady	Periodic	Momentary
Constant	Intermittent	Transient

2. What kinds of things relieve your pain?

3. What kinds of things increase your pain?

Part 4: How Strong Is Your Pain?

People agree that the following 6 words represent pain of increasing intensity. They are:

0	1	2	3	4	5
None	Mild	Discomforting	Distressing	Horrible	Excruciating

To answer each question below, write the number of the most appropriate word in the space beside the question.

1. Which word describes your pain right now? _____
2. Which word describes it at its worst? _____
3. Which word describes it when it is least? _____
4. Which word describes the worst toothache you ever had? _____
5. Which word describes the worst headache you ever had? _____
6. Which word describes the worst stomach-ache you ever had? _____

Qualitative Interview Guide Regarding Subject's Feelings about Receiving Acupuncture

1. What made you decide to join this study on acupuncture?
 - a. Tell me about any past experiences you had with acupuncture
 - b. Do others in your life use acupuncture?
 - c. Not satisfied with your level of pain?
 - d. Heard acupuncture is used to treat pain.
2. What were your expectations for getting acupuncture prior to participating in this study?
3. Think about your overall acupuncture experience, how would you describe your experience?
 - a. What do you think was happening in your body?
 - b. Did you learn anything from the process of getting acupuncture? What did you learn?
4. Describe how acupuncture affected your pain
 - a. Did anything change about how you think about or relate to your pain after going through acupuncture treatments?
5. Did anything about getting acupuncture surprise you?
6. How is the acupuncture healthcare experience different from other healthcare experiences you have had?
7. How did you feel about the acupuncturist?
 - a. Did the acupuncturist treat any medical issues other than pain? What was that like?
8. Tell me the reasons you would or would not continue to get acupuncture in the future.
9. Is there anything else you would like us to know about how acupuncture affected you and your overall experience?

Protocol Acceptability Scale for Treating Sickle Cell Disease with Acupuncture *

(select the most appropriate answer)

1. Was participating in this study too hard?
 Not hard at all
 Somewhat hard
 Too hard
2. Were the study instructions easy to understand?
 Easy to understand
 Somewhat hard to understand
 Too hard to understand
3. Were the study questions easy to see?
 Easy to see
 Somewhat hard to see
 Too hard to see
4. Did you feel rushed to complete this study?
 Not rushed at all
 Somewhat rushed
 Too hard to complete
5. Did you enjoy being in this study?
 Enjoyed participating
 Somewhat enjoyed participating
 Did not enjoy participating
6. What did you think of getting acupuncture?
 I liked it
 I did not like it
 I didn't like it or not like it
7. Did you think acupuncture was painful?
 It was not painful
 It was painful
8. Would you get acupuncture again?
 I would get it again
 I would not get it again
9. Do you think this study will be well received by other adults with sickle cell disease?
 Others will enjoy being in this study
 Others will somewhat enjoy being in this study
 Others will not enjoy being in this study
10. Do you think the study was:
 Too short
 Too long
 Right length

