6.0 Study Design and Procedures

- This study is an unblinded, uncontrolled feasibility study.
- All subjects will receive acupuncture.
- Baseline measures will be taken prior to insertion of the acupuncture needles.
- The research assistant will confirm the subject's assigned code number before the start of each acupuncture session.
- The subject will lay face up on the acupuncture exam table.
- The acupuncturist will swab each of 18 acupuncture points with alcohol.
- Needle insertion will then be performed with a tapping in technique. The needles will be retained for 30 minutes; they will be twirled 3 times throughout the treatment. The needles will then be pulled.
- After the 10th acupuncture treatment the subject will complete data collection tools.

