7.0 Expected Risks/Benefits

- Expected Risks: There is a risk of bruising or bleeding after the acupuncture needle is withdrawn. There is a risk that they may experience a negative reaction from acupuncture and thereby experience worse symptoms from participation in the study. If potential subjects are afraid of needles, they may not want to participate although the needles are very small. There is risk that some of the questions in the questionnaires may make the subject uncomfortable, nervous or tired. There is also the risk of loss of privacy or confidentiality, but we will avoid this and all other risks as much as possible.
- Expected Benefits: There may be no benefit to individual subjects, but the knowledge gained from this study is expected to help providers better manage SCD pain by having a better understanding of whether or not acupuncture reduces the pain of SCD.

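### Interview question 4 takes an effect of acupuncture on pain as given, which makes an answer of no change harder to give

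*Combined protocol and SAP*

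**What the plan says.** Question 4 of the interview guide in Appendix B reads "Describe how acupuncture affected your pain". Its one sub-question, 4a, asks "Did anything change about how you think about or relate to your pain after going through acupuncture treatments". Question 9 closes the guide with "Is there anything else you would like us to know about how acupuncture affected you and your overall experience". Question 8, by contrast, is two-sided: "Tell me the reasons you would or would not continue to get acupuncture in the future".

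Section 6.0 states the design: "This study is an unblinded, uncontrolled feasibility study". Section 7.0 gives as the expected benefit a better understanding of whether acupuncture reduces sickle cell pain. The table in Section 8.0 describes the interview as covering subjects' feelings about receiving acupuncture. The same table schedules PROMIS and the McGill Pain Questionnaire at both time points. Section 9.0 plans descriptive statistics and reports pain outcomes before and after treatment. It does not say how the interviews will be coded or summarised.

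**The concern.** Question 4 does not ask whether pain changed. It asks for a description of an effect and names the cause. The study hopes to inform whether acupuncture reduces pain, and here the question leaves out the *whether*.

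Every subject knows that they received acupuncture, and no untreated or sham group gets the same interview. If some subjects with unchanged pain offer a small effect because the question expects one, nothing in the design would reveal it. Section 2.0 says the study should supply acceptability data and protocol revisions for a later randomised trial. Plain accounts of no change are useful for that purpose, and this wording may thin them out.

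**Working it through.** No formula applies. The plan states no figure that depends on this question, so the check is a reading of the guide and of the other instruments.

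**Step 1. Which main questions concern an effect on pain, and which assume an effect?**

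| Question | Subject | Effect on pain? | Assumes acupuncture had an effect? |
|---|---|---|---|
| 1 | Reasons for joining | No (pain appears only as a possible motive) | No |
| 2 | Prior expectations | No | No |
| 3 | Overall experience, open | No | No |
| 4 | Effect on pain | **Yes** | **Yes** |
| 5 | Surprises | No | No |
| 6 | Difference from other health care | No | No |
| 7 | The acupuncturist | No (7a concerns issues other than pain) | No |
| 8 | Reasons to continue or not | No | No |
| 9 | Anything else, general effect | Not specifically | **Yes** |

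One of the nine main questions is about the effect on pain, and it assumes one. Question 9 repeats the assumption in general terms.

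**Step 2. Does 4a repair question 4?** It is neutral in form, but it asks how the subject thinks about or relates to pain, not whether the level of pain changed. A subject could answer no to 4a and still have reported an effect under question 4.

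**Step 3. Which answers does question 4 allow on its own terms?**
- *It helped*: a direct answer.
- *It made it worse*: an equally direct answer, because the verb names no direction.
- *It made no difference*: possible, but only by contradicting the premise.

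So the wording disfavours one answer of the three, no change.

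**Step 4. Do other instruments ask subjects whether pain changed with acupuncture?**
- The Acceptability Scale asks whether acupuncture was painful, not whether pain changed.
- The Credibility/Expectancy Questionnaire is scheduled only at baseline and records expectation.
- PROMIS pain intensity, pain interference and the McGill questionnaire ask about current pain or pain in the past 7 days, at both time points, without mentioning acupuncture. Improvement, worsening and no change can all show in the difference.

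Change in pain is therefore measured neutrally elsewhere. The subject's own account of that change rests mainly on question 4.

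**The case against.** The strongest reply is that question 4 should not be read alone. It follows a neutral opening, "Think about your overall acupuncture experience, how would you describe your experience", and is followed by 4a, an open question on surprises and the two-sided question 8. In an open interview, *it didn't* is an easy reply. The interview is about feelings, the pain scores are collected separately, and the feasibility aim of recruitment, retention and completion does not depend on it. All of this stands. It limits the consequence but does not make the wording neutral.

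Three stronger readings are tempting, and the documents do not support them.

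- *The question hides worsening.* Section 7.0 warns that subjects may "thereby experience worse symptoms from participation in the study", so a reader might infer that question 4 suppresses such reports. It does not, since worsening answers the question as directly as improvement.
- *The bias can be expressed as a share of the 15 subjects.* The plan nowhere says that interviews will be coded as helped or not helped and reported as a proportion, so there is no such share to distort.
- *The probes under question 1 are leading too*, for example "Not satisfied with your level of pain". They are lettered sub-items beneath an open question on why the subject joined. Nothing says they are read out before the subject has answered freely.

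**Conclusion.** The point holds as a minor wording defect. Question 4 is the only main question on the effect on pain. It presupposes an effect of acupuncture, and so makes no change harder to report in a study with neither blinding nor a control group. The reach is limited to the qualitative account of perceived benefit, and no figure or planned analysis changes.

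The documents give no basis for a size. That the wording alters any subject's answer is a reasonable expectation about interviews, not something the documents show. The conclusion also assumes that interviewers put question 4 as written, since the guide gives no instruction to rephrase it. The schedule marks the interview at both time points, but the point concerns only the one after treatment, when question 4 can be answered.

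**What to change.** Keep question 4 open and make it neutral, for example: *Describe how, if at all, your pain changed over the weeks of the study (better, worse or no different), and what you think explains that.* This names all three outcomes and leaves the attribution to the subject. It remains a request to describe, not a closed choice. Leave 4a as it is.

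In question 9, insert the same qualifier, so that it asks *how, if at all, acupuncture affected you*.

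The cost is a minor revision of the interview form, with no added visits, staff or measures. If interviews have already been done with the present wording, the answers to questions 4 and 9 will be slightly less comparable across the two forms. In that case, record which form each subject received.
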